The primary endpoint will be determined as change from baseline LDL-C for all patients on 100 mg MGL-3196 from week 4-12 relative to placebo the “100 mg group” (a similar calculation will be made for those who continue from Week 4-12 on the 60 mg dose, the “60 mg group”); secondary endpoints will include LDL-C lowering in all patients on MGL-3196 relative to placebo (for 12 weeks), and LDL-C lowering according to exposure to MGL-3196. Additional secondary endpoints will include change from baseline in other lipids including ApoB, nonHDL-C, Lp(a), and TGs.

The exposure levels of statins will also be assessed at baseline and Week 2 (two time points) and pre-dose PK samples will be collected throughout the study. Patients will record the exact time they took the statin the evening before the clinic visit. This will allow the unblinded clinical pharmacologist to determine if there is any unexpected effect on statin exposure related to MGL-3196 dosing. Any changes in statin levels will be monitored by the DSMB and medical monitors.

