2.2 Secondary Objectives

The secondary objectives of this study are the following:

- To evaluate the safety profile, including any changes in thyroid axis hormones, and tolerability of once-daily oral dosing regimen of MGL-3196 versus placebo after 12 weeks in patients with HeFH;
- To determine the effect of once-daily oral dosing regimen of MGL-3196 versus placebo for 12 weeks on the percent change from baseline on the following assessments in patients with HeFH:
 - Non-high-density lipoprotein cholesterol (non-HDL-C),
 - Apolipoprotein B (ApoB),
 - Total cholesterol/high-density lipoprotein cholesterol (HDL-C) ratio,
 - Triglycerides,
 - Lipoprotein(a),
 - Apolipoprotein A1 (ApoA1)/ApoB ratio, and
 - Lipoprotein particle assessment; and
- To determine the effect of once-daily oral MGL-3196 100 mg versus placebo for 12 weeks on the absolute change from baseline in LDL-C in patients with HeFH.
- To determine the effect of all patients (100 and 60 mg groups) on per cent change from baseline in LDL-C
- To determine the effect of exposure to MGL-3196 on LDL-C lowering.

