7 EFFICACY ASSESSMENTS

The primary efficacy parameter is mean percent change from baseline in LDL-C.

The secondary efficacy parameters include the following:

- Mean percent change from baseline in non-HDL-C, ApoB, TC/HDL-C ratio, triglycerides, lipoprotein(a), ApoA1/ApoB ratio, and lipoprotein particle assessment; and
- Absolute percent change from baseline in LDL-C.
- Mean percent change from baseline in LDL-C for all patients on study drug (60-100 mg)
- Mean per cent change from baseline in LDL-C according to MGL-3196 exposure

The exploratory efficacy parameters include the following:

- [REDACTED]
- [REDACTED]
- [REDACTED]

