10.2 Statistical Methods

10.2.1 Analysis of Efficacy

10.2.1.1 Primary efficacy analysis

The primary efficacy variable will be the change in LDL-C from baseline to Week 12. Summary statistics (number of patients, mean, standard deviation, median, minimum, and maximum) at all visits and change from baseline will be provided. The primary efficacy analysis will be analyzed with an analysis of covariance (ANCOVA) model with treatment as a factor and baseline LDL-C as a covariate. Determinations for the 100 (and 60) mg groups will be based on all 12 weeks of the study, including the first two weeks (Week 0-2) in which all patients were on 100 mg and the second two weeks (Week 2-4) when all patients down-titrated to 60 mg. The assigned group (60 or 100 mg) will be based on the dose at Week 4 to Week 12. For any patients in the ITT Population with a missing primary efficacy parameter, the last observation carried forward method will be used. The multiplicity (MGL-3196 100 mg versus placebo and MGL-3196 60 mg versus placebo) will be controlled by Dunnett's Test. The primary efficacy analysis will be performed based on the ITT Population and repeated based on the Per Protocol Population.

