2. STUDY OBJECTIVES AND STUDY DESIGN

2.1 Study Objectives

2.1.1 Primary Objective

The primary objective of this study is to determine the effect of each of two separate treatment groups (the “100 mg group” and the “60 mg group”) of once-daily oral dose of MGL-3196 and matching placebo on the percent change from baseline in low-density lipoprotein cholesterol (LDL-C) in patients with heterozygous familial hypercholesterolemia (HeFH).

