2.1.2 Secondary Objectives

The secondary objectives of this study are the following:

- To evaluate the safety profile, including any changes in thyroid axis hormones, and tolerability of once-daily oral dosing regimen of MGL-3196 versus placebo after 12 weeks in patients with HeFH;
- To determine the effect of once-daily oral dosing regimen of MGL-3196 versus placebo for 12 weeks on the percent change from baseline on the following assessments in patients with HeFH:
 - Non-high-density lipoprotein cholesterol (non-HDL-C),
 - Apolipoprotein B (ApoB),
 - Total cholesterol (TC)/high-density lipoprotein cholesterol (HDL-C) ratio,
 - Triglycerides,
 - Lipoprotein(a),
 - ApoB/Apolipoprotein A1 (ApoA1) ratio, and
 - Lipoprotein particle assessment;
- To determine the effect of once-daily oral dose of MGL-3196 versus placebo for 12 weeks on the absolute change from baseline in LDL-C in patients with HeFH;
- To determine the effect of all patients (100 and 60 mg groups) on percent change from baseline in LDL-C; and
- To determine the effect of exposure to MGL-3196 on LDL-C lowering.

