3.7.2 Primary Efficacy Analyses of LDL-C

The primary efficacy variable will be the percent change in LDL-C from baseline to Week 12. Summary statistics (number of patients, mean, standard deviation, median, minimum, and maximum) at all visits and change and percent change from baseline will be provided.

The primary efficacy variable, the percent change in LDL-C from baseline to Week 12, will be analyzed using an analysis of variance (ANOVA) model with treatment (MGL-3196 or placebo) as a factor based on the mITT population. For any patients in the mITT Population with a missing primary efficacy variable, the last post-baseline observation carried forward (LOCF) method will be used. The least-squares mean, 95% confidence interval, and p-value will be provided for the comparison of MGL-3196 versus placebo.

Sample SAS® code is provided below:

```
*****

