** PCHG = Percent change in LDL-C from Baseline to Week 12      **
** TRT = Treatment group where 0 = placebo, 1= MGL-3196           **
*****
PROC GLM;
  CLASS TRT;
  MODEL PCHG = TRT;
  LSMEANS TRT / e pdiff=control("0") cl;
RUN;
```

In addition to the percent change from baseline to Week 12 in LDL-C, the change in LDL-C from baseline to Week 12 will be analyzed using an analysis of covariance (ANCOVA) model with treatment as a factor and the baseline value as a covariate. For any patients in the mITT Population with a missing primary efficacy variable, the LOCF method will also be used.

Sample SAS® code is provided below:

```
*****

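### The stated primary objective is each dose group's effect, but the SAP's only primary test is pooled MGL-3196 versus placebo, which both documents list as secondary; the alpha and sample size still describe the dose tests

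*SAP*

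**What the plan says.** **Objective.** Protocol 2.1 and SAP 2.1.1 use the same words. The aim is to "determine the effect of each of two separate treatment groups", the 100 mg group and the 60 mg group, on percent change in LDL-C.

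**Protocol analysis.** Section 10.2.1.1 makes two comparisons: "The multiplicity (MGL-3196 100 mg versus placebo and MGL-3196 60 mg versus placebo) will be controlled by Dunnett's Test".

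**SAP analysis.** Section 3.1 bases the efficacy and safety analyses on MGL-3196 and placebo. Section 3.7.2 fits one two-level factor: "The least-squares mean, 95% confidence interval, and p-value will be provided for the comparison of MGL-3196 versus placebo". The sample code confirms it: "TRT = Treatment group where 0 = placebo, 1= MGL-3196". There is no dose level and no Dunnett adjustment.

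**Rank of the pooled comparison.** Protocol 1.2.2 says "secondary endpoints will include LDL-C lowering in all patients on MGL-3196 relative to placebo (for 12 weeks"). Protocol 2.2 has the secondary objective "To determine the effect of all patients (100 and 60 mg groups) on per cent change from baseline in LDL-C", and SAP 2.1.2 repeats it: "To determine the effect of all patients (100 and 60 mg groups) on percent change from baseline in LDL-C". Protocol 7 lists "Mean percent change from baseline in LDL-C for all patients on study drug (60-100 mg") as a secondary parameter, and so does SAP 2.3.1.

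**Rank of the dose groups in the SAP.** They appear in 3.7.3, the subgroup section, by final dose. That section calls its analyses descriptive and makes no multiplicity adjustment.

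**Sizing.** SAP 4, like protocol 10.2.4, plans 27 completers per group for 90% power at 0.025. The 0.025 is explained by there being two dosing regimens to compare with placebo.

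**The concern.** One contrast is both primary (SAP 3.7.2) and secondary (SAP 2.1.2 and 2.3.1). The contrasts named in the primary objective are descriptive. The only significance level the plan states belongs to those descriptive contrasts; for the pooled test a two-sided 0.05 can only be inferred from the 95% confidence interval.

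At stake is what the trial may conclude. If the pooled result is clear and one dose group's is not, or the reverse, the documents give no agreed answer on whether the primary objective was met.

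The two kinds of contrast also differ in quality. Randomisation is 2:1 to study drug or placebo (protocol 5.3). The dose groups are formed later, in active patients only, from the Week 2 drug level (protocol 5.1). Comparing either group with all placebo patients is therefore not a randomised comparison.

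**Working it through.** **1. Inputs** (SAP 4, same in protocol 10.2.4): difference 20 percentage points, SD 20, 27 completers per group, alpha 0.025, 70 active and 35 placebo randomised. Sidedness is not stated and is taken as two-sided. No dropout rate is stated.

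**2. Formula.** Two-sample t-test with noncentrality 20 / (20 × √(1/n1 + 1/n2)) and n1 + n2 − 2 degrees of freedom; power from the noncentral t distribution.

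**3. The plan's own figure.** For 27 versus 27, noncentrality is 1/√(2/27) = 3.67 on 52 df, and power at two-sided 0.025 is 91.0%. With 26 versus 26 it is 89.8%. So 27 is the smallest size reaching 90%. The figure is correct, for one dose-versus-placebo test.

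**4. The SAP's actual primary test.** Suppose 27 of the 35 placebo patients complete (27/35 = 77%) and 2:1 holds, giving 54 active completers.

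| Active vs placebo | Noncentrality | Power at 0.05 | Power at 0.025 |
|---|---|---|---|
| 54 vs 27 | 4.24 | 98.7% | 97.3% |
| 70 vs 35 | 4.83 | 99.8% | 99.4% |

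The pooled test is well powered at either level, but neither row is in the plan.

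**5. Is the dose-test sizing secured?** With no dropouts, 27 in each dose group out of 70 needs each group's share to lie between 27/70 = 38.6% and 43/70 = 61.4%. Neither document gives the share expected at or above the 1,500 ng/mL cut. The nearest figure is in protocol 1.2.2: about 25–30% of patients above target exposure at 100 mg. That is a different quantity. Taken purely as an assumed share for the 60 mg group, at two-sided 0.025 it gives:

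| Set | 60 mg vs placebo | Power, 60 mg | 100 mg vs placebo | Power, 100 mg |
|---|---|---|---|---|
| Completers (54 and 27) | 14–16 vs 27 | 76–80% | 38–40 vs 27 | 95–96% |
| All randomised (70 and 35) | 18–21 vs 35 | 87–90% | 49–52 vs 35 | about 99% |

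Under that assumption the share falls outside 39–61%, and among completers the 60 mg test misses the planned 90%.

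**The case against.** **The pooled contrast is the better primary.** This stands, with one qualification. It follows the randomised arms, but the SAP's mITT population (3.2.1) requires at least two weeks of drug and a valid lipid value at Week 2 or later, so some randomised patients are left out. Being the better choice is a reason to adopt it openly; it does not remove the conflict.

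**The SAP governs the analysis, and 3.1 makes its basis clear.** The operative test is indeed clear. But SAP 2.1.1, 2.1.2, 2.3.1 and 4 contradict it within the same document, so precedence over the protocol does not settle the matter.

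**The change may be recorded elsewhere.** The SAP text available, from its introduction onward, gives no rationale, and the visible part of its contents list shows no section on changes from the protocol. SAP 1 covers only deviations from the SAP itself. However, front matter was removed from the copy reviewed, so a dated revision note cannot be ruled out. One cannot say that the sponsor left the change unrecorded.

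**A reader might infer that the primary was switched after results were seen.** The documents do not support that. SAP 3.7.4 shows that screening and baseline LDL-C had been looked at, but those values carry no information on treatment effect. Protocol 5.3 keeps the sponsor and those evaluating data blinded until database lock, SAP 3.2.2 plans the deviation review before unblinding, and SAP 3.10 plans no interim analysis. These do not date the change, but they point towards a blinded SAP.

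**Conclusion.** The inconsistency is real and must be fixed, because the choice of primary comparison decides whether the trial met its objective. The finding rests on the conflict between SAP 2.1.1 and 3.7.2, and between SAP 3.7.2 and protocol 10.2.1.1. It does not depend on when or why the change was made.

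It is not a power deficit. The stated 27 per group reproduces, and the pooled test has 98.7–99.8% power at two-sided 0.05. These figures assume the plan's difference and SD of 20; the lower one also assumes 27 placebo completers at 2:1. The 76–90% for the 60 mg test depends on borrowing the 25–30% exposure figure as the size of that group. It shows that the dose-test sizing is not guaranteed, not that it would fail.

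**What to change.** In the SAP (2.1.1, 2.1.2, 2.3.1, 3.7.2 and 4):

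- Name one primary comparison: MGL-3196 versus placebo by randomised arm, percent change in LDL-C at Week 12, two-sided 0.05.
- Remove that comparison from the secondary lists.
- Replace the two-dose sizing at 0.025 with the power of this test: 98.7% with 54 versus 27 completers (assumption stated) and 99.8% with 70 versus 35.
- Keep the 100 mg and 60 mg results in 3.7.3 as descriptive, non-randomised estimates with confidence intervals. Use one definition of dose group: protocol 10.1 goes by the dose from Week 4 to Week 12 and SAP 3.7.3 by final dose. These can differ because TSH-driven down-titration is allowed (SAP 2.2), so the passages must be reconciled.
- State the change from protocol 10.2.1.1, its reason and its date relative to unblinding, unless the removed front matter already does so.

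In the protocol, align the primary objective, endpoint lists, Dunnett rule and sample-size text.

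**Cost.** A SAP revision and a protocol amendment, which under protocol 13.1 goes through the same review and approval as the original protocol. No new patients or data. The trial gives up any confirmatory dose-specific claim, which SAP 3.7.3 already concedes.

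The two documents also differ on population and model (ITT with ANCOVA in the protocol, mITT with ANOVA in the SAP). That needs its own resolution, as a separate point.

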** PCHG = Percent change in LDL-C from Baseline to Week 12      **
** TRT = Treatment group where 0 = placebo, 1= MGL-3196           **
*****
PROC GLM;
  CLASS TRT;
  MODEL PCHG = TRT;
  LSMEANS TRT / e pdiff=control("0") cl;
RUN;
```

In addition to the percent change from baseline to Week 12 in LDL-C, the change in LDL-C from baseline to Week 12 will be analyzed using an analysis of covariance (ANCOVA) model with treatment as a factor and the baseline value as a covariate. For any patients in the mITT Population with a missing primary efficacy variable, the LOCF method will also be used.

Sample SAS® code is provided below:

```
*****
** CHG = Change in LDL-C from Baseline to Week 12      **
** TRT = Treatment group where 0 = placebo, 1= MGL-3196           **
** BASE = Baseline LDL-C                                     **
*****
PROC GLM;
```

```
CLASS TRT;  
MODEL CHG = TRT BASE;  
LSMEANS TRT / e pdiff=control("0") cl;  
RUN;
```

The same analysis models for Week 12 LDL-C are also used to analyse the percent change and change in LDL-C from baseline at Week 2 and Week 4 LOCF.

The primary efficacy analysis will be performed based on the Per Protocol Population to evaluate the robustness of the primary efficacy analysis.

Other imputation method for missing values of Week 12 LDL-C will be evaluated, including multiple imputation and Mixed Model for Repeated Measurements (MMRM) method based on the mITT population. The multiple imputation method will use statin group (80 mg Atorvastatin, 20/40 mg Rosuvastatin, or No/Low Dose Statin), baseline and all the post-baseline valid LDL-C values as references for the imputation with the monotone missingness assumption. The MMRM method will include treatment and visit as factors, and treatment by visit interaction.

3.7.3 Subgroup Analysis of LDL-C

The subgroup analysis of LDL-C will be based on the mITT population. Since the analyses are for descriptive purposes only, no adjustments will be made for multiplicity.

The analysis of LDL-C will be performed based on MGL-3196 exposure group. In the analysis of LDL-C based on MGL-3196 exposure group, the patients who are taking MGL-3196 will be categorized into higher and lower exposure groups. The same ANOVA and ANCOVA models will be used, with pairwise comparisons between each exposure group versus placebo will be provided.

The analysis of LDL-C will also be performed based on SHBG group. In the analysis of LDL-C based on SHBG group, the patients who are taking MGL-3196 will be categorized into groups with higher increase or lower increase of SHBG from baseline to Week 12. Patients who are taking MGL-3196 but do not have Week 12 SHBG values will not be included. The same ANOVA and ANCOVA models will be used, with pairwise comparisons between each exposure group versus placebo to be provided.

The final dose of MGL-3196 (100 mg or 60 mg) will also be used to repeat the primary efficacy analysis. Similar to the exposure group, an analysis will be performed, but with the final dose of MGL-3196 to categorize patients who are taking MGL-3196.

The primary efficacy analysis of LDL-C will be repeated based on the following subgroups:

- Statin subgroup (80 mg Atorvastatin, 20/40 mg Rosuvastatin, or No/Low Dose Statin);
- Exposure group, SHBG group, in combination with statin subgroup;
- Gender subgroup (male, or female);
- Exposure group, SHBG group, in combination with gender subgroup;
- Baseline LDL-C value (<100 mg/dL, or \geq 100 mg/dL);
- Statin and baseline LDL-C subgroup;

- Exposure group, SHBG group, Final MGL-3196 dose group, in combination with baseline LDL-C subgroup;
- Baseline BMI value (<25 kg/m², or ≥25 kg/m²; and <30 kg/m², or ≥30 kg/m²);
- Exposure group, SHBG group, Final MGL-3196 dose group, in combination with baseline BMI subgroup;
- Average TSH between baseline and screening subgroup (<2 mIU/L, or ≥2 mIU/L);
- Exposure group, SHBG group, Final MGL-3196 dose group, in combination with average TSH between baseline and screening subgroup;

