2.3 Study Endpoints

2.3.1 Efficacy Variables

The primary efficacy parameter is mean percent change from baseline in LDL-C.

The secondary efficacy parameters include the following:

- Mean percent change from baseline in non-HDL-C, ApoB, TC/HDL-C ratio, triglycerides, lipoprotein(a) (Lp(a)), ApoB/ApoA1 ratio, Apolipoprotein CIII (ApoCIII), and lipoprotein particle assessment;
- Absolute change from baseline in LDL-C;
- Mean percent change from baseline in LDL-C for all patients on study drug (60-100 mg); and
- Mean percent change from baseline in LDL-C according to MGL-3196 exposure.

The exploratory efficacy parameters include the following:

- [REDACTED]
- [REDACTED]
- [REDACTED]
- [REDACTED]

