3.7.5 Secondary and Exploratory Endpoint Analyses

All the secondary and exploratory endpoints will be summarized and analyzed based on the mITT Population. In addition to the overall analysis, analyses by exposure group, [REDACTED] group, and final study drug dose will also be performed. No adjustments will be made for multiplicity.

For continuous variables, the ANCOVA model specified for the primary analysis will be used. For patients with missing values at Week 12, the LOCF method will be used for imputation. Normality will be tested for the model residuals.

For Lp(a), statin subgroup and baseline Lp(a) subgroup (≤ 10 or > 10 nmol/L) will be summarized and analyzed, as well as other cut-offs (70 nmol/L) and quartile analyses as appropriate. The statin subgroup will also be explored for ApoB, ApoCIII, and other lipids if appropriate. Other subgroup analysis will also be conducted as needed.

For triglycerides and [REDACTED], a logarithm transformation may be performed prior to fitting the ANCOVA model for change in triglycerides and [REDACTED]. The treatment comparisons will be transformed back to the difference in percent change from baseline. If the model residuals for the ANCOVA model of the logarithm transformed data still do not satisfy the normality assumption, the Wilcoxon rank-sum test will be performed as the main analysis to compare the percent change from baseline to Week 12. In addition to the Wilcoxon rank-sum test, the Hodges-Lehmann method will be used to estimate the median difference and its corresponding 95% confidence interval.

For certain efficacy endpoints, the MMRM method may be used to test the robustness of the results with treatment and visit as factors, and treatment by visit interaction. The treatment difference at Week 12 will be estimated from the MMRM.

For categorical variables, Fisher's exact test will be used to compare the percentages between MGL-3196 doses versus placebo at each post-baseline visit.

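### LDL-C by exposure: each exposure group is compared only with placebo, so no higher-versus-lower difference with a confidence interval is planned for the secondary objective on exposure

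*SAP*

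**What the plan says.** SAP 2.1.2 gives as a secondary objective "To determine the effect of exposure to MGL-3196 on LDL-C lowering", and Protocol 2.2 has the same item. SAP 2.3.1 lists the matching secondary parameter: "Mean percent change from baseline in LDL-C according to MGL-3196 exposure".

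The analysis is in SAP 3.7.3, where "the patients who are taking MGL-3196 will be categorized into higher and lower exposure groups". The ANOVA and ANCOVA are then repeated, "with pairwise comparisons between each exposure group versus placebo will be provided". The section also states: "Since the analyses are for descriptive purposes only, no adjustments will be made for multiplicity". SAP 3.7.5 extends "analyses by exposure group" to the other secondary and exploratory endpoints and adds no new contrast.

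The models being reused are those of SAP 3.7.2, where "The least-squares mean, 95% confidence interval, and p-value will be provided for the comparison of MGL-3196 versus placebo". The sample code there requests differences from the placebo control.

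Nothing else fills the gap. SAP 3.9 summarises concentrations descriptively and relates them to drug interactions and safety, not to LDL-C. Protocol 10.2.1.2 says only that the same ANCOVA applies to continuous secondary variables. Neither document plans a higher-versus-lower comparison, a trend test or an exposure-response model for LDL-C.

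**The concern.** The objective is about a difference inside the active arm: do patients with higher exposure lower LDL-C more than patients with lower exposure? Each planned comparison has a different null, namely no drug effect in that exposure group. Rejecting it mostly repeats the primary result in a smaller sample.

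The p-values therefore follow the size of the drug effect and the group sizes. If both groups beat placebo, that fits equal responses and also fits clearly different ones. If only one does, a reader may see an exposure effect that no planned estimate supports. Because the design sets the Week 4–12 dose from the Week 2 drug level, how response relates to exposure is a natural question for this Phase 2 trial.

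**Working it through.** **Inputs.** From SAP section 4: effect -20 points versus placebo, SD 20, 70 active and 35 placebo randomised, 27 completers per group. The two-sided 0.05 level is inferred from the 95% intervals and the absence of adjustment. The share of patients in each exposure class is not given, so several splits are shown.

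**The plan's own figure.** With 27 per group, SE = 20 × √(2/27) = 5.44 and noncentrality = 20/5.44 = 3.67. At two-sided 0.025 the noncentral t gives 91.0% power, against 89.8% at 26 per group. So 27 is the smallest n reaching 90%, and the SAP figure is reproduced.

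**Planned comparisons when exposure makes no difference.** Set both exposure groups at -20. For a group of size n against placebo of size m, SE = 20 × √(1/n + 1/m) and noncentrality = 20/SE. For 35 v 35, SE = 4.78 and noncentrality = 4.18. For 16 v 27, SE = 6.31 and noncentrality = 3.17. Joint rates come from simulating the three-group ANOVA with pooled variance.

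| Higher / lower / placebo | Higher v placebo | Lower v placebo | Both | At least one | Higher v lower |
|---|---|---|---|---|---|
| 35 / 35 / 35 | 98.5% | 98.5% | 97.3% | 99.8% | 5.0% |
| 20 / 50 / 35 | 94.2% | 99.4% | 93.9% | 99.8% | 5.0% |
| 27 / 27 / 27 | 95.2% | 95.3% | 91.6% | 98.8% | 5.0% |
| 16 / 38 / 27 | 88.0% | 97.5% | 86.6% | 98.8% | 5.0% |

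A plain two-sample t-test for 16 v 27 gives 87.2%, hence the range of about 87–99% per test.

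**Dependence on drug effect.** With 35/35/35 and a common effect in both groups, each test rejects in about 87% of trials at -15, 55% at -10 and 5% at zero. Exposure is irrelevant in every one of these cases, and only the drug effect changes.

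**Reading the significance pattern.** At a uniform -12, exactly one group is significant in 28% (35/35/35), 35% (20/50/35), 32% (27/27/27) and 37% (16/38/27) of trials. These count both directions. Higher significant and lower not is 14% for 35/35/35, 7% for 20/50/35 and about 28% for 50/20/35.

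**What can already be read off.** (higher − placebo) − (lower − placebo) = higher − lower, because placebo cancels. The point difference is therefore in the planned output. Its uncertainty is not shown by the two versus-placebo intervals, because they share one placebo group.

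**The direct contrast.** Half-width = t × 20 × √(1/n_higher + 1/n_lower), with pooled degrees of freedom:

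| Higher / lower / placebo | SE | 95% CI half-width | Power for a 10-point gap |
|---|---|---|---|
| 35 / 35 / 35 | 4.78 | 9.5 | 54% |
| 20 / 50 / 35 | 5.29 | 10.5 | 46% |
| 27 / 27 / 27 | 5.44 | 10.8 | 44% |
| 16 / 38 / 27 | 5.96 | 11.9 | 38% |

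**Limit of the 5% rate.** It assumes that the classes are prognostically alike. If they differed by 5 points for reasons other than exposure, the 35/35/35 contrast would reject in about 18% of trials. At 10 points it would reject in about 54%.

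**The case against.** The strongest reply is that SAP 3.7.3 calls these analyses descriptive, and that the declared parameter is mean change by exposure class, which the plan delivers. Neither document states a null of equal response. The least-squares means come with confidence limits, so a reader can subtract them and, for the ANOVA, rebuild a standard error by hand. The code shown is sample code for a two-level treatment factor, and table specifications sit in separate documents that were not available.

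Much of this stands, and it rules out several stronger readings that a reader might infer:

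- *The objective gets no valid answer.* Not supported: the point difference is recoverable from planned output, and the SAP adopts no rule based on which group is significant.
- *The 99% is a false-positive rate.* It is ordinary power for the drug effect. It depends on the full -20 in both groups and on an assumed 0.05 level.
- *The direct contrast would settle the question with high power.* That needs a gap between classes as large as the whole planned drug effect. Protocol 1.2 reports similar lipid effects across 80–200 mg in healthy volunteers and gives no basis for a 20-point gap.
- *The direct contrast has a nominal error rate.* Exposure class is set after randomisation, and the Week 4–12 dose depends on the Week 2 level, so the classes are tied to later dose by design.

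What the reply does not remove is the missing interval. A descriptive answer still needs the relevant estimate with its uncertainty. Keeping only the versus-placebo comparisons does not avoid the non-randomised grouping, since they use the same groups.

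**Conclusion.** The point holds in limited form. The only planned comparisons of LDL-C by exposure are against placebo, and they measure drug effect within each class. At the SAP's planned -20 and SD 20, with no exposure difference, each rejects in about 87–99% of trials and at least one in about 99%. With a weaker drug effect the figures fall. Patterns of one significant and one non-significant group are common at intermediate effects, about 28–37% at -12 for the splits shown. These figures rest on the assumed 0.05 level, normal data with a common SD, and assumed exposure splits. The structural conclusion does not depend on the split.

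The consequence is confined to a secondary objective: its most relevant quantity has no planned confidence interval. The primary analysis and its error control are not affected.

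**What to change.** In SAP 3.7.3, fit the existing model with three levels (placebo, lower, higher) and add the higher-minus-lower least-squares mean difference in Week 12 percent change with its 95% CI. Do the same where SAP 3.7.5 repeats the exposure-group analysis. State that any comment on exposure rests on that estimate, and keep the versus-placebo contrasts as context. Label the estimate a descriptive, non-randomised association, because exposure class is set after randomisation and the Week 4–12 dose depends on the Week 2 level.

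The cost is one contrast line in the program and a few sentences of SAP text, with no new data or patients. The drawbacks are limited precision (half-width about 9.5–12 points, power about 38–54% for a 10-point gap) and possible confounding. The interval will often be too wide to exclude a moderate exposure difference, and the report should say so.
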